5.3.3.1 Surgery

Surgery will be scheduled following restaging imaging either during week 3 or week 4 of treatment (no sooner than 72 hrs and no longer than 7 days following administration of the 2nd cycle of

nivolumab when tolerated). The exact surgical procedure and perioperative care is at the discretion of the treating surgeon as per standard of care, but should in general include resection of the primary lesion and an ipsilateral or bilateral neck dissection with or without a reconstruction or graft.

As evidenced by patients with melanoma treated with checkpoint blockade, patients who derive clinical benefit from these agents may, in some cases, experience a transient tumor “flare” prior to a prolonged systemic response. It is unknown whether this will occur in patients treated on this trial. Since this transient flare could potentially be indicative of an anti-tumor immune response, investigators are encouraged to proceed with treatment as per protocol; however, if there is symptomatic progression with significantly increased pain, airway compromise, or any other symptoms or exam findings deemed concerning by the treating physician then the patient may proceed to surgery early. As long as the patient has received experimental treatment he/she will be monitored and considered similar to other patients enrolled in this protocol.

5.3.3.2 Adjuvant treatment

The need for adjuvant treatment will be determined by the treating physicians based on the initial clinical staging in conjunction with pathology at the time of surgery and the patient’s performance status and medical comorbidities. If indicated, adjuvant treatment (radiotherapy with or without concurrent chemotherapy) will begin approximately 5-8 weeks following surgery as per standard of care.

5.4 Definition of Dose-Limiting Toxicity

Nivolumab, ipilimumab, and the combination of these two agents have been evaluated in prior phase I protocols and are being evaluated specifically in patients with SCCHN. However, although this is not a phase I protocol, the use of these drugs and the combination in the preoperative setting is relatively novel, and therefore we plan to include a safety-run-in to ensure that treatment is well tolerated in this setting. A separate safety run in will be performed for each cohort. As described in detail Section 14, the safety run-in will first be performed in the nivolumab single agent cohort, using the definitions and window period defined in this section. Once the safety run in has completed successfully with single agent nivolumab, patients will be enrolled to the nivolumab/ipilimumab cohort safety run-in.

The DLT window for this study will be the period between the first treatment and the time of surgery. We will also closely monitor toxicities in the post operative period and during adjuvant treatment; however, given the significant variability in surgical procedure and adjuvant treatment and significant toxicities associated with this when administered as SOC, these will not be considered DLTs. Dose-limiting toxicity (DLT) is based on the CTEP Active Version of the NCI Common Terminology Criteria for Adverse Events (CTCAE Version 4.0). A DLT will be defined as follows:

A patient in either cohort that is medically unable to undergo planned surgery because of toxicities deemed to be the result of experimental treatment or where surgery is delayed by >1 month beyond the originally scheduled date.

Other DLTs will be graded according to the National Cancer Institute's CTCAE version 4.0 (http://evs.nci.nih.gov/ftp1/CTCAE/CTCAE_4.03_2010-06-14_QuickReference_8.5x11.pdf). A DLT is any event that: a) occurs during the DLT evaluation period; and b) is possibly, probably, or definitely related to the administration of nivolumab and/or ipilimumab; and c) fulfills any of the following criteria:

1. Any Grade ≥ 3 pneumonitis, neurological event or uveitis.
2. Any Grade 2 pneumonitis, neurological event or uveitis, with the *following exception*:
 - Grade 2 pneumonitis, neurological event or uveitis that downgrade to Grade ≤ 1 within 3 days after onset, whereby maximal supportive care, including systemic corticosteroids, is permitted.
3. Any *other* Grade ≥ 3 toxicity, with the *following exceptions*:
 - Grade 3 irAEs that downgrade to Grade ≤ 2 within 3 days, or to Grade ≤ 1 or baseline within 14 days after onset, whereby maximal supportive care, including systemic corticosteroids, is permitted.
 - Grade 3 colitis that downgrades to Grade ≤ 2 within 7 days after onset, whereby maximal supportive care, including systemic corticosteroids, is permitted.
 - Grade 3 asymptomatic endocrinopathy, managed with or without systemic corticosteroid therapy and/or hormone replacement therapy.
 - Grade 3 inflammatory reaction attributed to a local antitumor response (e.g., inflammatory reaction at sites of metastatic disease, lymph nodes, etc.).
 - Grade 3 fatigue for ≤ 7 days.
 - Grade 3 infusion-related reaction (first occurrence and in the absence of steroid prophylaxis) that resolves within 6 hours with appropriate clinical management.
 - Liver transaminase elevation ≤ 8 times ULN that downgrades to Grade ≤ 2 (≤ 5 times ULN) within 7 days after onset, whereby maximal supportive care, including systemic corticosteroids, is permitted.
 - Total bilirubin ≤ 5 times ULN that downgrades to Grade ≤ 2 (≤ 3 times ULN) within 7 days after onset, whereby maximal supportive care, including systemic corticosteroids, is permitted.
 - Grade ≥ 3 neutropenia that (1) is not associated with fever or systemic infection, (2) does not require medical intervention, and (3) improves to Grade 2 within 7 days.
 - Grade 3 and 4 lymphopenia.
 - Grade 3 thrombocytopenia that (1) is not associated with clinically significant bleeding, (2) does not require medical intervention, and (3) improves to Grade 2 within 7 days.

CONFIDENTIAL

This document is confidential. Do not disclose or use except as authorized.

- Isolated Grade 3 electrolyte abnormalities that are not associated with clinical signs or symptoms and are reversed with appropriate maximal medical intervention within 3 days.
- Any pre-existing laboratory abnormality that deteriorates to Grade 3/4, but where the increment of deterioration is considered not clinically significant by both investigator and sponsor.

Immune-related AEs (irAEs) are defined as AEs of immune nature (i.e., inflammatory) in the absence of a clear alternative etiology. In the absence of clinical abnormality, repeat laboratory testing will be conducted to confirm significant laboratory findings prior to designation as a DLT.

While rules for adjudicating DLTs are specified above, an AE that is Grade < 3 or listed as exempt above may also be defined as a DLT after consultation with the sponsor and Investigators, based on the emerging safety profiles of nivolumab and ipilimumab. Likewise, subjects who become not evaluable for DLT because they discontinued or interrupted treatment due to toxicities other than DLTs may be counted as DLT subjects.

5.5 General Concomitant Medication and Supportive Care Guidelines

The treating physicians may deliver supportive care as indicated or as specified above in section 5.2, 5.3 and the IB.

Medications or vaccinations specifically prohibited in the exclusion criteria are not allowed during the ongoing trial. If there is a clinical indication for one of these or other medications or vaccinations specifically prohibited during the trial, discontinuation from trial therapy or vaccination may be required. The final decision on any supportive therapy or vaccination rests with the investigator and/or the subject's primary physician.

Acceptable Concomitant Medications

All treatments that the investigator considers necessary for a subject's welfare may be administered at the discretion of the investigator in keeping with the community standards of medical care. All concomitant medication will be recorded on the case report form (CRF) including all prescription, over-the-counter (OTC), herbal supplements, and IV medications and fluids. If changes occur during the trial period, documentation of drug dosage, frequency, route, and date may also be included on the CRF.

All concomitant medications received within 28 days before the first dose of study treatment should be recorded. Relevant concomitant medications administered after the last dose of trial treatment should be recorded for SAEs as specified in Section 11.1.2.

Prohibited Concomitant Medications

Subjects are prohibited from receiving the following therapies during the Screening and Treatment Phase of this trial:

- Antineoplastic systemic chemotherapy or biological therapy
- Immunotherapy not specified in this protocol

- Investigational agents other than nivolumab with or without ipilimumab
- Any systemically active oral, injected, or implanted hormonal method of contraception except for progesterone coated intrauterine devices (IUDs) that had been previously implanted.
- Live vaccines within 28 days prior to the first dose of trial treatment and while participating in the trial. Examples of live vaccines include, but are not limited to, the following: measles, mumps, rubella, varicella/zoster, yellow fever, rabies, BCG, and typhoid vaccine.
- Systemic glucocorticoids for any purpose other than to modulate symptoms from radiation or an event of clinical interest of suspected immunologic etiology. The use of physiologic doses of corticosteroids may be approved after consultation with the Sponsor.

Subjects who, in the assessment by the investigator, require the use of any of the aforementioned treatments for clinical management should be removed from the trial. Subjects may receive other medications that the investigator deems to be medically necessary.

There are no prohibited therapies during the Post-Treatment Follow-up Phase.

The following treatments are permitted throughout the duration of the study treatment phase and during follow-up:

- Standard therapies for pre-existing medical conditions unless listed as prohibited therapy below. Any medication intended solely for supportive care (e.g., analgesics, anti-diarrheal, anti-depressants) may be used at the investigator's discretion. Antiemetics and anti-diarrheal medications should not be administered prophylactically before initial treatment with study drugs. At the discretion of the investigator, prophylactic antiemetic and anti-diarrheal medication(s) may be used as per standard clinical practice before subsequent doses of study drugs or before, during or after radiation treatment.
- Anticoagulants - Anticoagulation with heparin, heparin derivatives, and/or warfarin may be given at the discretion of the treating physician. Coagulation parameters should be checked at least once monthly, or more frequently at discretion of treating physician.
- Pain medications administered per standard clinical practice are acceptable while the patient is enrolled in the study.

Patients who experience toxicities should be treated symptomatically as clinically indicated. Medications that are considered necessary for the subject's welfare and that are not expected to interfere with the evaluation of study treatment or be restricted may be given at the discretion of the investigator. Ancillary treatments will be given as medically indicated.

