3. PARTICIPANT SELECTION

3.1 Eligibility Criteria

Participants must meet the following criteria on screening examination to be eligible to participate in the study:

1. Pathologically confirmed squamous cell carcinoma of the oral cavity. Clinical stage \geq T2 (primary tumor greater than 2 cm in size) and/or evidence of regional nodal involvement by clinical exam or imaging
2. Only patients 18 years and older are eligible. There is no upper age limit but the patients must be able to medically tolerate the regimen. Adverse event data are currently unavailable on the use immune checkpoint blockade for participants < 18 years of age, and thus children are excluded from this study
3. ECOG performance status \leq 1 (see Appendix A)
4. Patients must be a surgical candidate (e.g. their disease must be considered resectable before any treatment and must have no serious medical contraindications that definitively preclude undergoing general anesthesia)
Ability to understand and the willingness to sign a written informed consent document
5. Women of childbearing potential (WOCBP) must agree to use appropriate method(s) of contraception (see Appendix B). WOCBP should use an adequate method to avoid pregnancy for 23 weeks (30 days plus the time required for nivolumab to undergo five half-lives) after the last dose of investigational drug. WOCBP is defined as any woman or adolescent who has begun menstruation and is not post-menopausal. A post-menopausal woman is defined as a woman who is over the age of 45 and has not had a menstrual period for at least 12 months

CONFIDENTIAL

This document is confidential. Do not disclose or use except as authorized.

6. Women of childbearing potential must have a negative serum or urine pregnancy test (minimum sensitivity 25 IU/L or equivalent units of HCG) to be scheduled within 24 hours prior to the start of nivolumab
7. Men who are sexually active with WOCBP must agree to use any contraceptive method (see Appendix B) with a failure rate of less than 1% per year. Men receiving nivolumab and who are sexually active with WOCBP will be instructed to adhere to contraception for a period of 31 weeks after the last dose of investigational product. Women who are not of childbearing potential (ie, who are postmenopausal or surgically sterile as well as azoospermic men do not require contraception)
8. Participants must have normal organ and marrow function as defined below:

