Appendix B: Methods of Contraception

At a minimum, subjects must agree to use one highly effective OR one less effective method of contraception as listed below:

Highly Effective Methods Of Contraception

Highly effective methods of contraception have a failure rate of < 1% when used consistently and correctly. WOCBP and female partners of male subjects, who are WOCBP, are expected to use one of the highly effective methods of contraception listed below. Male subjects must inform their female partners who are WOCBP of the contraceptive requirements of the protocol and are expected to adhere to using contraception with their partner. Contraception methods are as follows:

1. Progestogen only hormonal contraception associated with inhibition of ovulation.
2. Hormonal methods of contraception including oral contraceptive pills containing combined estrogen + progesterone, vaginal ring, injectables, implants and intrauterine devices (IUDs) such as Mirena®
3. Nonhormonal IUDs, such as ParaGard®
4. Bilateral tubal occlusion
5. Vasectomised partner with documented azoospermia 90 days after procedure

Vasectomised partner is a highly effective birth control method provided that partner is the sole sexual partner of the WOCBP trial participant and that the vasectomised partner has received medical assessment of the surgical success.

6. Intrauterine hormone-releasing system (IUS).
7. Complete abstinence

Complete abstinence is defined as the complete avoidance of heterosexual intercourse.

Complete abstinence is an acceptable form of contraception for all study drugs and must be used throughout the duration of the study treatment (plus 5 half-lives of the investigational drug plus 30 days).

It is not necessary to use any other method of contraception when complete abstinence is elected.

Subjects who choose complete abstinence must continue to have pregnancy tests

Acceptable alternate methods of highly effective contraception must be discussed in the event that the subject chooses to forego complete abstinence.

The reliability of sexual abstinence needs to be evaluated in relation to the duration of the clinical trial and the preferred and usual lifestyle of the subject.

Less Effective Methods Of Contraception

1. Diaphragm with spermicide
2. Cervical cap with spermicide
3. Vaginal sponge with spermicide
4. Male or female condom with or without spermicide*

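### Section 5.5 bars oral, injected and implanted hormonal contraception that Appendix B accepts for the same women

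*Combined protocol and SAP*

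**What the plan says.** Section 5.5 introduces its prohibited list with "Subjects are prohibited from receiving the following therapies during the Screening and Treatment Phase of this trial". One entry is "Any systemically active oral, injected, or implanted hormonal method of contraception except for progesterone coated intrauterine devices (IUDs) that had been previously implanted". No reason is attached. The ban is limited in time, because the same section later says "There are no prohibited therapies during the Post-Treatment Follow-up Phase".

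Criterion 5 in Section 3.1 says that women of childbearing potential "must agree to use appropriate method(s) of contraception (see Appendix B"), and adds that "WOCBP should use an adequate method to avoid pregnancy for 23 weeks" after the last dose.

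Appendix B asks for at least one listed method, from either its highly effective or its less effective group. Its introduction to the highly effective group covers female subjects as well as the female partners of male subjects. Item 1 of that group is "Progestogen only hormonal contraception associated with inhibition of ovulation". Item 2 begins "Hormonal methods of contraception including oral contraceptive pills containing combined estrogen + progesterone, vaginal ring, injectables, implants" and goes on to intrauterine devices. Item 5 of the less effective group is a progestogen-only pill.

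**The concern.** Two operative rules give opposite answers for the same woman at the same time. A site checking criterion 5 would accept a contraceptive pill, injection or implant. The same site checking concomitant medication against Section 5.5 would record a prohibited therapy. The text does not tell the site which rule governs, so sites could handle the same case differently.

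At stake is the clarity of a safety rule. A woman who stops her pill, injection or implant to comply with Section 5.5 may be giving up a method that Appendix B ranks as highly effective, around the time she is dosed. Section 2.1.1.1 describes nivolumab as a selective developmental toxicant in cynomolgus monkeys dosed from organogenesis to parturition. That exposure is not the two-dose schedule used here. It explains why the contraception rule should be unambiguous, but it does not measure the risk to these subjects.

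**Working it through.** No figure in the plan is involved and no arithmetic applies. The check compares the two rules on who is bound, when, and for which methods, and then looks for text that reconciles them.

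**Who.** Section 5.5 binds subjects. Appendix B covers female subjects as well as partners of male subjects. The rules overlap for female subjects of childbearing potential. Partners are outside Section 5.5 and are unaffected.

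**When.** Section 5.5 applies during screening and treatment and lapses in follow-up. Criterion 5 is an entry criterion, and its requirement runs on for 23 weeks after the last dose. Appendix B limits none of its hormonal methods to a particular phase. The rules therefore overlap throughout screening and treatment.

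**Which methods**, for a female subject during screening and treatment:

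| Method | Section 5.5 | Appendix B | Result |
|---|---|---|---|
| Combined pill (highly effective item 2) | Barred | Listed | Conflict |
| Injectable (item 2) | Barred | Listed | Conflict |
| Implant (item 2) | Barred | Listed | Conflict |
| Progestogen-only, ovulation-inhibiting (item 1) | Barred if oral, injected or implanted | Listed, no route named | Conflict for those routes |
| Progestogen-only pill (less effective item 5) | Barred | Listed | Conflict |
| Hormonal IUD or intrauterine system (items 2 and 6) | Progesterone-coated IUD exempt only if already in place | Listed without that limit | Agree for a progesterone-coated IUD already in place; otherwise a mismatch |
| Vaginal ring (item 2) | Not named | Listed | Unclear; not relied on here |
| Non-hormonal IUD, tubal occlusion, vasectomised partner, abstinence (items 3, 4, 5, 7) | Not barred | Listed | Agree |
| Barrier methods (less effective items 1 to 4) | Not barred | Listed | Agree |

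**Reconciling text.** None was found in Section 3, Section 5.5 or Appendix B. Section 5.5 gives the investigator or primary physician the last word on supportive therapy and vaccination, but contraception is not described as either. Its permission for other medically necessary medications sits beside the specific ban and does not lift it.

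**The case against.** The strongest reply is that the rules can be read together. Appendix B is a menu from which one method is chosen. It also serves partners, whom Section 5.5 does not bind, and the weeks after the last dose, when nothing is prohibited. A narrower rule for screening and treatment could sit on top of that general list, and a woman who picks a non-hormonal method complies with both. On this view only a cross-reference is missing.

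Much of this stands. Joint compliance is possible, which is why the point is minor. It does not remove the conflict, because neither place mentions the other's restriction, and a woman who relies on Appendix B alone can breach Section 5.5.

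A reader might infer more than the documents support:

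- **That pill users must leave the trial.** Section 5.5 applies removal to subjects who, in the investigator's assessment, "require the use of any of the aforementioned treatments for clinical management should be removed from the trial". Elective contraception with listed alternatives would not ordinarily meet that condition.
- **That the conflict leaves women without adequate contraception.** Several highly effective non-hormonal methods satisfy both rules, and a negative pregnancy test is required within 24 hours before the first dose. Appendix B's acceptance of barrier methods exists whether or not Section 5.5 bans anything.
- **That the ban has a calculable length.** The end of the Treatment Phase is not defined. Section 5.3.1.3 allows a delayed dose until week 4 is reached, and the 7-day limit to surgery in Section 5.3.3.1 applies only when treatment is tolerated. A share of calendar days would not measure pregnancy risk in any case.

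**Conclusion.** The contradiction is real and minor. For oral, injected and implanted hormonal methods, Section 5.5 and Appendix B give a female subject opposite instructions during screening and treatment. There is a smaller mismatch over hormonal intrauterine devices that are not already in place.

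Those affected are women of childbearing potential who use, or would choose, one of these methods. They are some part of the 40 planned patients, and the documents give no count. The sample size, decision rules, endpoints and analyses are untouched.

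The conclusion rests on a literal reading of both texts. The consent pages and Investigator Brochures are not in the review copy, so a rationale for the ban may exist there.

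**What to change.** Delete the hormonal-contraception entry from the prohibited list in Section 5.5.

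If the sponsor has a reason to keep it, state that reason in Section 5.5 and annotate Appendix B for female subjects during screening and treatment:

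- Not permitted: oral, injected or implanted forms under highly effective item 1; the pills, injectables and implants in item 2; and less effective item 5.
- Permitted only if previously placed: hormonal intrauterine devices and systems (items 2 and 6).

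The choice between the two belongs to the sponsor and investigators. Either is a wording amendment needing the IRB approval that Section 13.1 requires, with no change to sample size, visits or analysis. Whether the consent form needs a matching edit cannot be judged from the review copy.

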5.3.1.4 Discontinuation criteria

Tumor assessments should continue as per protocol even if study drug is discontinued.

Treatment should be permanently discontinued for the following:

Any Grade 2 drug-related uveitis or eye pain or blurred vision that does not respond to topical therapy and does not improve to Grade 1 severity within the re-treatment period OR requires systemic treatment.

Any Grade 3 non-skin, drug-related adverse event lasting > 7 days, with the following exceptions for drug-related laboratory abnormalities, uveitis, pneumonitis, bronchospasm, neurologic toxicity, hypersensitivity reactions, and infusion reactions:

Grade 3 drug-related uveitis, pneumonitis, bronchospasm, neurologic toxicity, hypersensitivity reaction, or infusion reaction of any duration requires discontinuation.

Grade 3 drug-related laboratory abnormalities do not require treatment discontinuation except:

Grade 3 drug-related thrombocytopenia > 7 days or associated with bleeding requires discontinuation

Any drug-related liver function test (LFT) abnormality that meets the following criteria require discontinuation:

AST or ALT > 8 x ULN

Total bilirubin > 5 x ULN

Concurrent AST or ALT > 3 x ULN and total bilirubin > 2 x ULN

Any Grade 4 drug-related adverse event or laboratory abnormality, except for the following events which do not require discontinuation:

Isolated Grade 4 amylase or lipase abnormalities that are not associated with symptoms or clinical manifestations of pancreatitis and decrease to < Grade 4 within 1 week of onset.

Isolated Grade 4 electrolyte imbalances/abnormalities that are not associated with clinical sequelae and are corrected with supplementation/appropriate management within 72 hours of their onset.

Any adverse event, laboratory abnormality, or intercurrent illness which, in the judgment of the Investigator, presents a substantial clinical risk to the subject with continued nivolumab dosing.

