Stop the nivolumab infusion, begin an IV infusion of normal saline, and treat the subject with diphenhydramine 50 mg IV (or equivalent) and/or paracetamol 325 to 1000 mg (acetaminophen); remain at bedside and monitor subject until resolution of symptoms. Corticosteroid or bronchodilator therapy may also be administered as appropriate. If the infusion is interrupted, then restart the infusion at 50% of the original infusion rate when symptoms resolve; if no further complications ensue after 30 minutes, the rate may be increased to 100% of the original infusion rate. Monitor subject closely. If symptoms recur then no further nivolumab will be administered at that visit. Administer diphenhydramine 50 mg IV, and remain at bedside and monitor the subject until resolution of symptoms. The amount of study drug infused must be recorded. The following prophylactic premedications are recommended for future infusions: diphenhydramine 50 mg (or equivalent) and/or paracetamol 325 to 1000 mg (acetaminophen) should be administered at least 30 minutes before additional nivolumab administrations. If necessary, corticosteroids (recommended dose: up to 25 mg of IV hydrocortisone or equivalent) may be used.

For Grade 3 or Grade 4 symptoms: (Severe reaction, Grade 3: prolonged [ie, not rapidly responsive to symptomatic medication and/or brief interruption of infusion]; recurrence of symptoms following initial improvement; hospitalization indicated for other clinical sequelae [eg, renal impairment, pulmonary infiltrates]). Grade 4: (life threatening; presser or ventilator support indicated).

Immediately discontinue infusion of nivolumab. Begin an IV infusion of normal saline, and treat the subject as follows. Recommend bronchodilators, epinephrine 0.2 to 1 mg of a 1:1,000 solution for subcutaneous administration or 0.1 to 0.25 mg of a 1:10,000 solution injected slowly for IV administration, and/or diphenhydramine 50 mg IV with methylprednisolone 100 mg IV (or equivalent), as needed. Subject should be monitored until the investigator is comfortable that the symptoms will not recur. Nivolumab will be permanently discontinued. The patient should be treated for therapy induced anaphylaxis. Remain at bedside and monitor subject until recovery from symptoms. In the case of late-occurring hypersensitivity symptoms (eg, appearance of a localized or generalized pruritus within 1 week after treatment), symptomatic treatment may be given (eg, oral antihistamine, or corticosteroids).

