5.6 Duration of Therapy

In the absence of DLTs study treatment is expected to continue until the second dose of nivolumab is administered. At that time, all subsequent cancer treatment will be administered as per standard of care.

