5.7 Criteria for Taking a Participant Off Protocol Therapy

Participants should also be removed from protocol therapy if any of the following occurs:

- Unacceptable adverse event(s)
- Participant demonstrates an inability or unwillingness to comply
- Participant decides to withdraw from the protocol therapy
- General or specific changes in the participant's condition render the participant unacceptable for further treatment in the judgment of the treating investigator
- Intercurrent illness that prevents further administration of treatment and/or would affect the assessment of the subject's clinical status to a significant degree
- Pregnancy

Participants will be removed from the protocol therapy when any of these criteria apply. The reason for removal from protocol therapy, and the date the participant was removed, must be documented in the case report form (CRF). Alternative care options will be discussed with the participant.

Information will be entered in OnCore when a participant is removed from protocol therapy.

In the event of unusual or life-threatening complications, participating investigators must immediately notify the Principal Investigator, [name], MPH at [contact] or at [name].

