5.9 Criteria for Taking a Participant Off Study

Participants will be removed from study when any of the following criteria apply:

- Lost to follow-up
- Withdrawal of consent for data submission
- Death

The reason for taking a participant off study, and the date the participant was removed, must be documented in the case report form (CRF).

The research team will update the relevant Off Treatment/Off Study information in OnCore.

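### Section 5.5 gives two different instructions for a treated patient who needs a prohibited drug: stop trial therapy, or leave the trial. It should say off protocol therapy, with follow-up continued.

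*Combined protocol and SAP*

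**What the plan says.** Section 5.5 deals with the same event twice. In its opening text, when a prohibited medication is clinically indicated, "discontinuation from trial therapy or vaccination may be required". After the list of prohibited drugs, which applies in the screening and treatment phase, it says that subjects who in the investigator's assessment "require the use of any of the aforementioned treatments for clinical management should be removed from the trial".

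Elsewhere the protocol separates two exits:

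- **Off therapy, Section 5.7:** "Participants should also be removed from protocol therapy if any of the following occurs". The list includes unacceptable adverse events, intercurrent illness and changes in the patient's condition. Need for a prohibited drug is not named.
- **Off study, Section 5.9:** "Participants will be removed from study when any of the following criteria apply". The criteria are loss to follow-up, withdrawn consent to submit data, and death.

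Two sections keep treated patients under observation. Section 5.3.1.4: "Tumor assessments should continue as per protocol even if study drug is discontinued". Section 5.3.3.1, on patients operated on ahead of schedule, has this sentence: "As long as the patient has received experimental treatment he/she will be monitored and considered similar to other patients enrolled in this protocol". Section 14 assesses volumetric response, and the other endpoints it lists, in everyone who starts protocol therapy, and divides responders by all patients treated in the arm.

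**The concern.** The two statements in Section 5.5 lead to different conduct. Under the first, a dosed patient stops drug and is still restaged, operated on and followed. Under the second, taken at its word, the patient leaves the trial, and the site may stop collecting study restaging, pathologic response, disease-free survival and overall survival. That patient would still count in the Section 14 denominator. The result would be missing data that the rest of the protocol is written to avoid. With 20 patients per arm and a threshold of 6 responders, a single missing response can matter at the boundary.

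**Working it through.** **1. Who is affected.**

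- Patients registered but never treated are outside the point. Section 4.1 cancels their registration, and Section 4.3 takes them off study at other sites.
- The ban covers screening and treatment. Under Section 5.6, "study treatment is expected to continue until the second dose of nivolumab is administered", so the ban may end before surgery, which Section 5.3.3.1 places 72 hours to 7 days after the second dose.
- Steroids for suspected immune events are exempt in Section 5.5, and physiologic doses may be approved. For a Grade 2 infusion reaction, Section 5.3.1.5 says "Corticosteroid or bronchodilator therapy may also be administered as appropriate".
- What remains is a dosed patient who needs a non-exempt drug, such as steroids for a non-immune reason, before the treatment phase ends.

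**2. Which instruction the rest of the protocol supports.** Sections 5.3.1.4, 5.3.3.1 and 14 all fit the first statement in Section 5.5 (off therapy, still assessed). None of them supports ending follow-up of a treated patient for this reason.

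**3. The plan's own figure.** Section 14 calls an arm promising with 6 or more responders of 20, said to give a one-sided 90% exact lower bound of at least 15%. The bound is the 0.10 quantile of Beta(x, n − x + 1):

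- x = 6, n = 20: 0.1659, above 15%. The stated rule is reproduced.
- x = 5, n = 20: 0.1269, below 15%.
- x = 5, n = 19 (lost patient dropped from the denominator instead): 0.1339, still below 15%.

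So one lost responder at the boundary changes the conclusion under either denominator. This is true of any missing responder and is not special to Section 5.5.

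**4. Illustrative cost per removed patient.** Assume removal is unrelated to response, no response measurement is obtained by any route, the patient counts as a non-responder, and the stop for no responses in the first 10 patients is ignored. The loss is P(Bin(20,p) ≥ 6) − P(Bin(19,p) ≥ 6), which equals P(Bin(20,p) = 6) × 6/20.

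| True rate p | No removal | One removal | Loss |
|---|---|---|---|
| 15% (plan's reference) | 0.0673 | 0.0537 | 0.0136 (1.4 points) |
| 30% (assumed) | 0.5836 | 0.5261 | 0.1916 × 0.3 = 0.0575 (5.7 points) |
| 40% (assumed) | 0.8744 | 0.8371 | 0.1244 × 0.3 = 0.0373 (3.7 points) |

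The loss is smaller if response is still read from pathology, or if removed patients are mostly progressing. The documents give no removal rate, so these figures cannot be turned into an expected effect on the trial.

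**The case against.** The strongest reply is that the sentence is loose wording for off therapy. It does not say that data collection stops, it uses *should* rather than *must*, and the text that follows refers to a post-treatment follow-up phase. Section 5.7 already covers intercurrent illness and changes in condition, which would catch many of these patients. All of this is fair and keeps the point small. It does not remove the disagreement within Section 5.5, and if off therapy is the intent, the amendment simply says so.

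Three stronger readings are tempting, and the documents do not support them.

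- A reader might infer a flat contradiction with Section 5.9. That section does not say its three criteria are the only ones, and Section 4.3 already takes untreated subjects off study for a reason not on its list. Absence from the list is supporting evidence, no more.
- A reader might infer that removal cuts short observation for dose-limiting toxicity, a co-primary endpoint whose window runs to surgery (Sections 5.4 and 14). But Section 10.1.1 makes everyone with at least one dose evaluable for toxicity, Section 6 collects adverse events from first dose to the visit 1 year after enrollment, and Section 11.8 follows events arising up to 30 days after the last study intervention until they resolve, stabilize or are judged irreversible, or the patient is lost to follow-up.
- A reader might add that Section 5.5 prohibits hormonal contraceptives that Appendix B lists as highly effective. That is a separate inconsistency and does not bear on how treated patients are followed.

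**Conclusion.** The point holds as a minor internal inconsistency. Section 5.5 gives sites two instructions for one event, and the second is at odds with Sections 5.3.1.4, 5.3.3.1 and 14. Data are lost only if a site follows that sentence over the others.

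The effect is probably small. The trigger is narrow, surgery goes ahead as standard of care, and Section 10.1.5.1 accepts scan, clinical exam or pathology for volumetric response. The losses of 1.4 to 5.7 points apply per removed patient and only under the assumptions stated, of which the absence of any response measurement is the least likely to hold. A conclusion that the response decision is materially biased would need a removal rate that the documents do not give.

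**What to change.** For subjects who have received at least one dose, replace removal from the trial in Section 5.5 with: *removed from protocol therapy and followed per protocol for restaging, surgical pathology, adverse events including DLTs to surgery, DFS and OS*. Add *need for a prohibited concomitant treatment* to the list in Section 5.7, which does not name it now. Leave registered but untreated patients to Sections 4.1 and 4.3.

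The cost is one reworded sentence and one added list item. Restaging, surgery and phone follow-up to 3 years are already planned (Sections 5.8 and 9), and no sample size or threshold changes. The downside is that a few followed patients will have taken a drug that could confound response. They can be flagged in the data and examined in a sensitivity analysis.
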